This Appendix describes the continuation of the 3 Dynamic Prevention Randomized studies (refer to section 9.2.1 of protocol) for a 48 week follow up period following re-consent for this CAB-LA extension. Persons who are already enrolled in the trials and were randomized to the intervention arm will be eligible to receive CAB-LA as one of the options in the “Dynamic prevention” model. Persons in the control arms will be eligible to receive CAB-LA if and when it is rolled out through in country programs. If CAB-LA is not available in country at the 48-week endpoint, all participants in the intervention arm will have the opportunity to continue in the study until Week 96, and participants who are currently on CAB-LA may continue through the extension. The study will end at Week 96, and by that time participants will be transitioned to in country prevention care. At 96 weeks, persons on CAB-LA will be transitioned to in country CAB-LA or to other prevention options if CAB-LA is not available. Prior to this transition, available in country options will be assessed by the study team. HIV prevention options will be discussed with each study participant by their Week 88 visit, with a plan established for the transition to the participant’s preferred prevention method in coordination with local health facilities to avoid interruption after their 96 weeks of study participation is completed.

The overall purpose of this extension is to 1) Determine if adding the option of CAB-LA as a prevention choice using a patient-centered HIV prevention delivery model increases prevention coverage (i.e. proportion of time that is covered by a biomedical prevention option, such as PrEP or PEP) compared to the standard-of-care in 3 ongoing randomized trials of Dynamic Choice Prevention in rural Uganda and Kenya; and, 2) Conduct a hybrid implementation study (Primary Objective Clinical and Secondary Objective Implementation) focusing on initial implementation of a patient-centered model for CAB-LA using the RE-AIM evaluation framework among persons randomized to the intervention arms.

A. Background and Rationale

Background: SEARCH Sapphire is an ongoing, NIH-funded study that is testing multi-disease and multi-sector interventions aimed at reducing HIV burden and improving health in rural Uganda and Kenya. Phase A is a portfolio of randomized prevention and treatment implementation studies that will inform a population-level study in Phase B (refer to section 3.0 of protocol).

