Ethical Considerations: The HPTN 084 study that showed efficacy of CAB LA for prevention included sites in both Uganda and Kenya. Applications for approval of CAB LA are under review in each of these countries. Thus, the information generated in this study on evaluating a dynamic prevention implementation strategy will be directly applicable. *During this proposed study extension, CAB LA is expected to become publicly available through Ministry of Health ("MoH") sponsored programs (in both Kenya and Uganda). UCSF is developing an additional extension to 96 weeks, which will examine longer-term safety and implementation data of CAB-LA. Should there be delay in rollout of the MoH programs, participants could continue in this additional extension phase. After the endpoint of the 96-week extension is reached, participants will be transitioned to a standard of care regimen, via local healthcare system, based on the investigator's clinical judgment and local country guidelines*

B. Hypothesis and Objectives

Hypotheses: A dynamic choice prevention model that includes a patient-entered CAB-LA delivery option will have higher levels of biomedical prevention coverage (assessed over 48 weeks following re-consent for the CAB-LA extension study) compared to the standard of care.

This hypothesis will be tested by comparing covered time between the intervention and control arms in the 3 ongoing randomized trials during the extension phase.

The secondary hypothesis: Addition of patient-centered CAB-LA into an ongoing dynamic choice prevention will improve biomedical prevention coverage (compared to dynamic choice prevention without CAB-LA).

These hypotheses will be tested by comparing covered time during the extension with the CAB-LA option to covered time prior to the extension among intervention arm participants.

We expect that incorporating the option of CAB-LA with patient-centered delivery for persons who self-identify at risk for HIV living in rural Uganda and Kenya will increase overall biomedical covered prevention time compared to the standard of care. In a population that has been offered -- and some of whom have taken up -- oral PrEP and PEP, we also expect to learn characteristics of who is most interested in CAB-LA, how our patient-centered CAB-LA delivery models work in different settings, and the cost of the delivery models in different settings.

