Outcomes: The primary outcome for the extension is the proportion of time covered by a biomedical prevention option during the 48 week follow-up period of the CAB-LA Extension; follow-up time will be censored at HIV diagnosis, death, or withdrawal. Biomedical covered time is defined as the proportion of follow-up time that each participant is covered by either PrEP (TDF/3TC or CAB-LA) or PEP. For TDF/3TC, covered time is defined using self-reported use; in a subset of participants who report PrEP use we will measure tenofovir drug levels using small hair samples to allow for calibration of self-reported measures. For CAB-LA, coverage begins 3 days after initial injection and continues 2 months + 7 days after last injection. For PEP, covered time is defined using self-reported use; in a subset of participants who report PEP use we will measure drug levels using hair samples to allow for calibration of self-reported measures. A secondary outcome for the extension is “at-risk covered time”, defined as the proportion of time that a participant reports being at risk of HIV infection during which they are covered by a biomedical prevention option. Incident HIV infections, defined by a prespecified testing algorithm, will be an additional secondary outcome.

Secondary outcomes of reach, effectiveness, adoption, implementation and maintenance will be evaluated using a mixed methods approach that includes surveys of participants, and health center providers and staff. Tertiary outcomes of knowledge, awareness and acceptability/satisfaction at the staff and provider level will be measured by surveys at the baseline, midpoint and end of the study. Measurement details delineated in Table 4 .

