Reach (Participant level)	Proportion of eligible participants who initiate CAB-LA weeks 0-48. Characteristics (including prior PrEP and PEP use) and attitudes (knowledge, acceptability and feasibility) of participants using CAB-LA	Demographics, CAB-LA dispensing logs Knowledge, Acceptability and Feasibility (Survey and IDI). Evaluation includes focus on equitable access by gender, education and SES.	CAB LA dispensing throughout follow-up Surveys and IDI: Week 0, 24 and week 48
Effectiveness (Participant level)	Impact of adding CAB-LA to Dynamic choice prevention on biomedical covered time (comparison of follow-up during the CAB-LA extension vs. follow-up time in Phase A trials prior to CAB-LA extension).	CAB-LA dispensing logs, PrEP and PEP use as defined for primary endpoint in extension.	Throughout follow-up
Adoption (Provider and staff level in different settings)	% of staff and providers invited that participate in the interventions, where participation is defined as i) participation in CAB-LA trainings; and ii) offering CAB-LA to participants. We will further assess the characteristics of participant vs. non-participant staff.	Training attendance rosters; CAB-LA dispensing logs	Throughout follow-up
Implementation (Provider and systems level)	Fidelity: Proportion of providers offering CAB-LA on appropriate schedule, appropriate provision of oral bridging Costing: Incremental cost of adding CAB-LA to dynamic choice prevention Adaptations: Type, timing and reasons they were made	CAB-LA and oral bridging dispensing logs Time in motion and program costing Adaptation logs	Throughout follow-up
Maintenance (adapted from standard RE-AIM to accommodate shorter follow-up) (Participant level)	Persistence on CAB-LA among participants who initiate CAB-LA Reasons for discontinuation of biomedical prevention or switching to other biomedical prevention option	CAB-LA dispensing logs Participant survey on reasons for discontinuation and switching	Throughout follow up

As a tertiary objective, we will also assess provider and staff Knowledge, Acceptability and Awareness via provider and staff surveys (Likert scales) and IDI at weeks 0, 24, and 48.

D. Schedule of Evaluations

For all participants, from the time of reconsenting at the start of study CAB-LA availability (Week 0), there will be study visits every 24 weeks for the duration of their participation.

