Participants will remain in the randomization arm they were assigned to at their initial DCP visit in Phase A (refer to section 9.1.1 of the protocol). Participants in the SOC arm will consent to return for two additional follow-up visits at weeks 24 and 48 following re-consent for the CAB-LA extension. Intervention participants that do not choose CAB-LA will consent to continue the quarterly study visits and Intervention participants that choose CAB-LA will have study visits that align with their injection visits (every 4 weeks for the first two months and then every 8-weeks thereafter). Intervention participants will have flexibility to switch between PrEP, PEP, and CAB-LA. Unlimited switches between biomedical prevention options, including between CAB-LA and oral, will continue to be permitted during the extension, both to reflect participant choice and to bridge planned missed doses of CAB-LA. Clients and providers will discuss options for prevention and risk during regular visits and interim visits, in addition to continuous provider trainings on offering choice and refreshers for clients. Changes in prevention choices will be documented in study eCRF forms, which will include the CAB-LA option. DCP intervention participants that choose the CAB-LA option will be informed about the visit schedule, side effects, and risks and benefits, before consenting. If CAB-LA becomes available via the Ministry of Health during the trial, persons in the control arm will be eligible as per standard of care.

Documentation of written informed consent and verbal consent will be recorded on informed consent logs for all study activities. The logs will contain the participant's study ID, clinic ID, initials, name, language of consent used, and whether the individual signed the document or provided a fingerprint in the case of written consents, or verbally affirmed their consent in the case of verbal consents.

Stored Samples and Associated Data Considerations

Plasma samples will be collected and stored for retrospective HIV testing and PK.

Hair samples collected from participants on PrEP, CAB-LA or PEP in the extension will be collected and stored for later measurements of HIV-prevention drug levels, which will be conducted at the UCSF Hair Analytical Lab in the United States.

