Our secondary objective to evaluate implementation will follow the RE-AIM framework and corresponding measures (defined in Table 4). Analyses assessing the primary measures of Reach, Adoption, Implementation and Maintenance will be based on standard descriptive statistics. Analyses to evaluate Effectiveness will compare covered time over the 48 week CAB-LA extension period to covered time prior to the CAB-LA extension among intervention participants. We will adjust for measured changes in participant characteristics between these two follow-up periods, using a TMLE designed for serial measures. Measures of control participants will also be used to adjust for temporal trends. We will test the null hypothesis that coverage of the DCP model with CAB-LA is the same as coverage of the DCP model without CAB-LA. We will again use a two-sided test at the 5% significance level. Primary analyses will again pool over trials, while secondary analyses will be stratified by trial. In addition, we will evaluate marginal and adjusted predictors of CAB-LA uptake and persistence. Our tertiary objective to evaluate changes in knowledge, awareness, and acceptability/satisfaction will be based on applying TMLE to survey data, accounting for repeated measures.

These analyses will be complemented with costing evaluations as well as participant and provider qualitative data from IDI.

All analyses of the community-based trial will account for clustering.

Pharmacokinetic analyses:

We will perform pharmacokinetic (PK) analyses of cabotegravir concentrations in plasma and small hair samples with two objectives. 1) To examine hair levels of CAB as predictors of effectiveness; 2) To examine factors associated with CAB PK variability and study correlations between CAB hair and plasma levels at the end of dosing intervals and during the PK tail. In the phase 3 trials of CAB LA, plasma concentrations of CAB did not fully explain CAB breakthrough infections (especially since failures occurred despite on-time injections) and therefore PK metrics, such as hair, that reflect longer-term exposure, may provide important insights regarding CAB exposure in addition to plasma. Drug concentrations of cabotegravir will be analyzed via liquid chromatography tandem mass spectrometry (LS-MS/MS) at the Hair Analytical Laboratory at UCSF. Plasma samples will be collected prior to each injection, while hair samples will be collected at weeks 8, 24, 32, and 48 after CAB LA start.

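### The test of adding CAB-LA uses control participants to remove time trends, but controls may receive CAB-LA on national roll-out; if that happens before week 48, the estimate is pulled towards zero

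*Protocol*

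**What the plan says.** All of this is in Appendix 18 of the protocol, the CAB-LA extension.

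- **Hypothesis.** Section H states: "We will test the null hypothesis that coverage of the DCP model with CAB-LA is the same as coverage of the DCP model without CAB-LA". Table 4 lists the same question as the RE-AIM Effectiveness measure: "Impact of adding CAB-LA to Dynamic choice prevention on biomedical covered time".
- **Comparison.** Section B describes a comparison within the intervention arm: "These hypotheses will be tested by comparing covered time during the extension with the CAB-LA option to covered time prior to the extension among intervention".
- **Role of controls.** Section H adds: "Measures of control participants will also be used to adjust for temporal trends".
- **Control access.** The introduction: "Persons in the control arms will be eligible to receive CAB-LA if and when it is rolled out through in country programs". Section E repeats it: "If CAB-LA becomes available via the Ministry of Health during the trial, persons in the control arm will be eligible as per standard of care".
- **Expected timing.** Under Ethical Considerations in Section A: "CAB LA is expected to become publicly available through Ministry of Health" programmes in both Kenya and Uganda during the extension.
- **Outcome.** Under Outcomes in Section C: "Biomedical covered time is defined as the proportion of follow-up time that each participant is covered by either PrEP (TDF/3TC or CAB-LA) or PEP". The definition does not differ by arm. Follow-up is censored at HIV diagnosis, death or withdrawal, and not at roll-out or at a control participant's first injection.

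The primary extension analysis is a different comparison: the whole DCP package including CAB-LA against standard of care, between arms.

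**The concern.** A control-based trend adjustment gives the effect of adding CAB-LA only if the control trend shows what would have happened without CAB-LA. Once controls can obtain it through the Ministry of Health (MoH), their extension coverage may include CAB-LA time. The adjustment would then treat that time as background trend and take it out of the intervention arm's gain.

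This matters because no other planned analysis answers the question. The primary comparison cannot separate CAB-LA from the rest of DCP. The trial-stratified analyses repeat the same contrast. The sensitivity analysis of covered time from CAB-LA alone changes the outcome and leaves the trend as it was. Nothing in Section H limits which control time or which products feed the trend.

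**Working it through.** **1. The plan's own figure.** Section J gives power only for the primary between-arm hypothesis. With 90% consent and 90% retention, 200 × 0.9 × 0.9 = 162 per arm. With SD 0.35 and an 11-point difference, SE = 0.35 × √(2/162) = 0.0389, and power = Φ(0.11/0.0389 − 1.96) = 0.807 (0.805 by t-test). This agrees with the stated figure of more than 80%. No effect size or power is given for the secondary hypothesis.

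**2. Direction of the bias.** Let g be the true gain from adding CAB-LA, t the common time trend, and c the net coverage that controls gain from national CAB-LA (new coverage, less any oral PrEP it replaces).

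- Intervention change: g + t
- Control change: t + c
- Trend-adjusted effect: (g + t) − (t + c) = g − c

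This assumes full subtraction. Section H specifies a TMLE for serial measures without giving its form, so c is an approximate upper limit on the attenuation. Any form that uses unrestricted control outcomes as the no-CAB-LA trend has the same direction of error.

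**3. Dependence on roll-out date.** Write c = g × r × f. Here r is the control gain per unit time after roll-out as a share of g, and f = (48 − roll-out week)/48. Both r and the roll-out week are assumptions. The table shows the effect recovered, in points, if g = 11. That value is borrowed from the primary calculation for illustration only.

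| Roll-out week | r = 0.10 | r = 0.25 | r = 0.50 | r = 1.0 |
|---|---|---|---|---|
| 0 | 9.9 | 8.3 | 5.5 | 0 |
| 24 | 10.5 | 9.6 | 8.3 | 5.5 |
| 36 | 10.7 | 10.3 | 9.6 | 8.3 |
| 48 or later | 11.0 | 11.0 | 11.0 | 11.0 |

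At week 24, for example, f = 0.5, so the share removed runs from 5% (r = 0.10) to 50% (r = 1.0).

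**4. Why no planned power loss can be stated.** Pool the three trials at 162 + 162 + 160 = 484 per arm, assume a between-period correlation of 0.5, and ignore clustering. Then SE = 0.35 × √(2 × 0.5) × √(2/484) = 2.25 points, and power = Φ((g − c)/SE − 1.96).

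| True effect g | c = 2 | c = 3 | c = 5 |
|---|---|---|---|
| 6.3 points (80% power when c = 0) | 48% | 31% | 8% |
| 11 points | 98% | 94% | 76% |

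The correlation matters too. With g = 6.3 and c = 2, power is 37% at correlation 0.3 and 69% at 0.7. The answer depends almost wholly on g, c and the correlation, and the documents supply none of them.

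**The case against.** The strongest reply is that the problem may never arise. The appendix plans for late roll-out: the introduction and Section D provide a re-consented schedule to week 96 if CAB-LA is not available in country at week 48. The closing section on participant protection says it is not yet approved in either country. Section D says the control arm's prevention care will not change, Section C says standard of care does not routinely offer PrEP or PEP, and no control uptake is forecast. The power section assumes 10% total control coverage in the community trial, so c = 5 would be half of that again. Section H also calls itself an overview, and none of the supplied SAPs covers the extension, which has its own registration. The bias, where present, is towards no effect.

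All of this stands as a limit on size and likelihood. It does not remove the gap, because the appendix names roll-out during the extension as its expectation and gives no rule for that case. Section B describes the comparison without controls, so the role of the control data needs stating in any event.

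A reader might go further and infer that this test will probably miss a real effect. The documents do not support that: the low powers in the working arise only when the true effect is placed exactly at its own 80%-power threshold. A reader might also infer that the primary analysis is biased. It is not, because CAB-LA obtained through national programmes is part of standard of care there. It would, however, narrow the contrast, so the primary is not untouched either.

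**Conclusion.** The point holds as a conditional one. If national roll-out comes before week 48 and controls gain c points of net covered time from CAB-LA, the trend-adjusted estimate of adding CAB-LA to DCP is attenuated by up to about c points. If roll-out comes at or after week 48, the bias is zero. The conclusion rests on control measures being used as the no-CAB-LA trend without restriction, which is how Section H reads. Because c, the roll-out date and the effect size for this hypothesis are not given, the figures above are illustrations and no planned power loss can be claimed. The matter concerns a secondary hypothesis, but the only one that isolates CAB-LA, and the handling should be fixed in advance.

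**What to change.** In Section H, for this secondary test only:

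1. Estimate the temporal trend from control follow-up before the date on which CAB-LA becomes available through the MoH in that country, matched to intervention follow-up over the same calendar months.
2. Report the full 48-week trend-adjusted estimate beside it.
3. Report control-arm CAB-LA use by country and calendar time, so that readers can judge c.

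Leave the primary comparison as it is, with all control coverage counted.

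A control trend built from oral PrEP and PEP alone is not a safe substitute. If controls switch from oral PrEP to CAB-LA, their oral coverage falls, the trend turns artificially downward, and the effect is overstated. Omit it, or show it only as a bound that can err in that direction.

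The cost is a change of wording. Control visits already ask which prevention methods were used, and the roll-out date in each country must be recorded. If roll-out is early, both arms lose person-months from this analysis and the restricted estimate describes earlier uptake rather than the full 48 weeks, which is why both estimates should be shown.
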